### **Rationale for targeting ER**

The finding that ER $\beta$  knock-out mice exhibit increased prostate and bladder hyperplasia suggests a potential role of ER $\beta$  in the development of urologic cancers. While ER $\alpha$  is expressed in 12.4%-18% of bladder cancers, we have found that ER $\beta$  is the predominant receptor expressed in several human bladder cancer cell lines and human bladder cancers comprised in tissue microarrays. An independent report from separate human tissue microarrays, analyzing a heterogeneous group of bladder tumors including different stages and grades from 2 institutions, also confirmed the expression of ER $\beta$  to be higher than ER $\alpha$ , and significantly higher expressed in high-grade/muscle-invasive tumors in comparison with low/non-muscle-invasive tumors. These data suggest that ER may be a rational target for intervention with selective estrogen receptor modulators (SERMs) for treatment and chemoprevention of bladder cancer.

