### **Specific Aims:**

**Aim 1.** Evaluate the efficacy of tamoxifen for treatment of low/intermediate-risk bladder tumors, assessing for the clinical response of the marker lesion, and analyzing the effects in tissue, in terms of affecting apoptosis and proliferation, while continuously monitoring for treatment toxicity.

**1a.** Evaluate the efficacy of tamoxifen for treatment of low/intermediate-risk bladder tumors, utilizing the RECIST criteria combined with the final biopsy of the marker lesion or the bed of the lesion in case of a complete response. (PRIMARY ENDPOINT)

**1b.** Evaluate the histopathologic effect of tamoxifen treatment in the tumor cells, assessing for the presence of necrosis, fibrosis, apoptosis and scar tissue.

**1c.** Evaluate the treatment effect in the histologic markers for apoptosis (TUNEL) and proliferation (Ki-67).

**1d.** Monitor treatment toxicity.

**Aim 2.** Evaluate the expression levels of ER $\alpha$  and ER $\beta$  (including splicing variants) before and after treatment with tamoxifen, in both normal and tumor tissues, and correlate the clinical response with the expression levels of these ERs.

**2a.** Report on and compare the pre and post-treatment expression levels of ER $\alpha$  and ER $\beta$  (including their splicing variants, more specifically ER $\beta$ -1, ER $\beta$ -2 and ER $\beta$ -5) in both normal and tumor tissues.

**2b.** Correlate the observed clinical effect, measured by the proportion of subjects that had complete or partial responses, with the pretreatment expression levels of ERs in tumor tissue.

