### **Overall study description**

Patients with primary or recurrent low/intermediate-risk papillary urothelial carcinoma of the bladder will undergo resection of all but one marker lesion, measuring at least 6mm but no greater than 10mm, and biopsy of normal-appearing mucosa. Patients with a solitary tumor will undergo only biopsy prior to treatment. A 2mm cold cup biopsy of the marker lesion will always be performed to rule out a potential high-grade lesion and for assessment of pretreatment immunohistochemistry expression levels of ER $\alpha$ , ER $\beta$ 1, Ki-67 (proliferation marker) and TUNEL (apoptosis marker). If there are multiple tumors, all lesions, except the marker lesion will be resected and sent for analysis. These patients will not receive single immediate post-operative intravesical instillation of mitomycin-C. They will then undergo a 12-week course of treatment with tamoxifen administered as a single daily oral dose of 20mg. At the completion of therapy, patients will undergo resection of the marker lesion (or biopsy of the tumor bed, if a complete response is observed) and biopsy of normal-appearing bladder mucosa again. Toxicity evaluations will be performed at the beginning (day 3), midway (week 6), and at completion of treatment (week 12), prior to resection of the marker lesion. A final assessment for toxicity will also be performed 30 days after completion of therapy as well as a second definitive resection of the marker lesion. Urine samples will be obtained with the index tumor in place (marker lesion), and after completion of treatment, at the time of definitive transurethral resection of the index tumor, as part of the standard clinical care of these patients, and at the discretion of the surgeon for assessment of urinary cytology. The urine samples will not be utilized for the research study. All normal-appearing bladder biopsies (pre and post-treatment), the additional tumors (in case of multiple lesions), and the definitive resection of the marker lesion (in the absence of response to therapy) will provide sufficient material for immunohistochemistry assessment of the expression levels of ER $\alpha$ , ER $\beta$ -1, ER $\beta$ -2, ER $\beta$ -5, Ki-67, and TUNEL, and also for RT-qPCR for mRNA analyses of ER $\alpha$ , ER $\beta$ -1, ER $\beta$ -2, and ER $\beta$ -5. The pretreatment biopsy of the marker lesion will be performed with a smaller biopsy forceps and will provide limited material, sufficient only for immunohistochemistry assessment of the expression levels of ER $\alpha$ , ER $\beta$ -1, Ki-67, and TUNEL.

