### **Statistical considerations on the proposed analyses of the secondary aims, including the biomarker experiments**

**Specific Aim 1b:** We will assess the histologic aspect of both normal tissue and the bladder cancer marker lesion biopsies before and after treatment and compare for the presence of fibrosis, scarring, tumor necrosis and apoptosis. These data will be measured and quantified using light microscopy so percent positivity can be evaluated. Comparisons will be made between normal and tumor tissues (independent samples analysis), and also between pre and post-treatment on both normal and tumor tissues (paired samples analysis) to evaluate the effect with tamoxifen treatment. Non-parametric tests will be utilized as appropriate.

**Specific Aim 1c:** We will compare pre and post-treatment levels of immunohistochemistry staining levels of both the normal tissue and the marker lesion to detect changes in expression of TUNEL and Ki-67, associated with treatment (paired samples analysis). Nuclear immunoreactivity will be assessed by light microscopy and percent positive stained nuclei calculated. The percentiles will be analyzed as a continuous variable. Just like above, non-parametric tests will be utilized as appropriate.

The modulation of pre vs. post-treatment biomarker endpoints will be summarized and compared using the paired t-test or nonparametric paired tests as appropriate for quantitatively measured biomarkers, including Ki-67, and TUNEL. Independent analyses will likewise be employed to compare these biomarkers measured between normal mucosa and marker bladder tumor. We will

also assess the correlations of TUNEL and Ki-67 with rates of positive response. Descriptive statistics will be calculated to summarize these biomarkers at pretreatment, post-treatment, difference from pre to post-treatment, and percent change from pre to post-treatment. Histologic effect will also be considered as a secondary endpoint in determining response to therapy. Histologic effect in the lesion will be summarized descriptively using frequencies and proportions before and after treatment.

**Specific Aim 1d:** Toxicity data will be presented and summarized using descriptive statistics, tabulated using frequencies and percentages.

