**Specific Aim 2a and 2b:** All data will be presented and summarized using descriptive statistics. The percentage of positive cells with nuclear immunoreactivity is recorded on a semi-quantitative scale: results are categorized as negative (< 10% cell labeling) or positive ( $\geq$  10% cell labeling). Normal breast tissue and transfected cells with known ER will be used as positive control and normal tissues such as liver and spleen, as well as cells transfected with empty vectors will be used as negative controls.

We will correlate pretreatment ER levels with the proportion of the positive response (composite endpoint of clinical PR and CR, and a final biopsy) of the marker lesion to determine associations with treatment effect. Specifically, Pearson's or Spearman's correlation coefficients will be calculated to estimate and test for significant correlations between the expression level of the ERs and the primary endpoint. Comparison of ERs expression levels from normal and bladder tumor tissues measured prior to treatment will also be performed using independent sample tests as described above. Non-parametric tests will be utilized as appropriate.

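### ER staining is coded negative or positive at 10%, although Aim 2 concerns expression levels and this stain is the only pretreatment ER measure in the marker lesion

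*Combined protocol and SAP*

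**What the plan says.** Under Specific Aims, Aim 2a is to "Report on and compare the pre and post-treatment expression levels of ER" alpha and ER beta in normal and tumour tissue. Aim 2b is to correlate response "with the pretreatment expression levels of ERs in tumor tissue".

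The section on analyses of the secondary aims, under Specific Aim 2a and 2b, sets the scale for ER staining: "The percentage of positive cells with nuclear immunoreactivity is recorded on a semi-quantitative scale: results are categorized as negative (< 10% cell labeling", and positive at 10% or above. The next paragraph plans Pearson or Spearman coefficients to test for "significant correlations between the expression level of the ERs and the primary endpoint". That endpoint is itself dichotomous (End-points/Statistical considerations).

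In the same section, Specific Aim 1c treats Ki-67 and TUNEL differently: "percent positive stained nuclei calculated. The percentiles will be analyzed as a continuous variable".

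Overall study description says that the pretreatment biopsy of the marker lesion "will provide limited material, sufficient only for immunohistochemistry assessment of the expression levels of" ER alpha, ER beta-1, Ki-67 and TUNEL. The Aim 2 procedures repeat this limit. They add RT-qPCR for ER mRNA on normal mucosa, on synchronous tumours and on the final resection of the marker lesion.

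**The concern.** The aims ask how much receptor is present, how that amount changes on tamoxifen, and whether it tracks response. A two-category record answers only whether a specimen lies above or below 10%. A fall from 80% to 15% counts as no change, while a rise from 9% to 11% counts as a change.

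This matters most for the marker lesion, the lesion in which response is judged. RT-qPCR cannot supply a pretreatment level there. Patients with a solitary tumour have no other tumour tissue before treatment. After treatment, Overall study description counts on sufficient marker-lesion material for RT-qPCR only when there has been no response.

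With at most 17 evaluable patients, a null ER result could reflect the cut-off rather than the biology. The plan gives no reason for handling ER differently from Ki-67 and TUNEL.

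**Working it through.** **What the plan gives.** It states no power, effect size, SD or distribution for any ER analysis, so there is no ER figure to reproduce. The inputs used are:

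- Maximum evaluable N = 17 and good response rate 0.30 (Sample Size).
- Ki-67 mean difference 1.101, SD of differences 1.41, two-sided alpha 0.05 (Ki-67 power calculation).
- ER alpha frequency: the plan's rationale says it "is expressed in 12.4%-18% of bladder cancers" (Rationale for targeting ER).

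**Benchmark.** For Ki-67 the standardised change is 1.101/1.41 = 0.78. A paired t-test at N = 17 (noncentral t) has power 85.6%, which matches the plan.

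**Aim 2a with yes/no coding.** Only patients who cross 10% contribute to a paired test. If k patients cross, all in one direction, the exact two-sided McNemar p-value is 2 x 0.5^k.

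- k = 5: p = 0.0625.
- k = 6: p = 0.031.

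So at least six of 17 must cross with none crossing back.

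**Aim 2b with yes/no coding.** When both variables are binary, Pearson and Spearman both equal phi. Take one ER-positive patient, who responds, and 3 responders of 17. The cells are 1, 0, 2 and 14.

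- phi = (1 x 14 - 0 x 2) / sqrt(1 x 16 x 3 x 14) = 14/25.9 = 0.54. The t approximation on 15 degrees of freedom gives p = 0.025.
- Fisher's exact test on the same table: p = 3/17 = 0.176.
- Two positives, both among the 3 responders: Fisher p = 3/136 = 0.022.

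The conclusion therefore turns on one patient and on the choice of test.

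**How many would be ER alpha positive?** Assume that 12.4-18% applies at this trial's 10% cut.

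- Expected positives: 17 x 0.124 = 2.1 to 17 x 0.18 = 3.1.
- Chance of one or none, (1-p)^17 + 17p(1-p)^16: 36% at 12.4% and 16% at 18%.

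With two or three positives, at most two or three patients can cross downwards, fewer than the six needed. Crossings upwards remain possible. The plan gives no such frequency for ER beta.

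**Illustrative power at N = 17.** These are simulations on an assumed normal scale. The ER-positive share and the pre/post correlation (0.3 to 0.7) are assumptions.

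| Comparison | Continuous percentage | Negative/positive |
|---|---|---|
| Fall of 0.78 SD of differences, 50-80% positive before treatment | about 86% (paired t) | 14-41% (exact McNemar) |
| Same fall, 20% positive before treatment | about 86% | 2-6% |
| Responders 1.5 SD higher, 30% respond, 20-50% positive | about 71% (Pearson) | 51-54% (phi); 36-40% (Fisher) |
| Same difference, 80% positive | about 71% | 3-5% (Fisher to phi) |

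**The case against.** The best defence is that the sentence opens by saying the percentage of positive cells is recorded and only then describes the categories. Nothing says that the percentage is thrown away. The planned correlations of expression level, and the difference and percent-change summaries promised in the general biomarker statistics, presuppose graded values. A reader might infer that the percentages will certainly be lost, and the documents do not prove that. What they do state is "results are categorized as negative (< 10% cell labeling) or positive", and no sentence names the percentage as the analysis variable for ER, as one does for Ki-67 and TUNEL. This part of the defence weakens the charge of lost data but leaves the mismatch in place.

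A reader might also infer that change and association cannot be seen at all. That is too strong. Crossings of 10% and a positive/negative association with response remain visible. RT-qPCR gives paired levels in normal mucosa, pretreatment levels in synchronous tumours, and levels in some post-treatment resections. Aim 2b refers to tumour tissue, not only to the marker lesion. The gap is therefore narrower: the marker lesion before treatment, and any pretreatment tumour mRNA in solitary-tumour patients.

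Nor does it follow that Aim 2b for ER alpha could not reach significance. That holds for Fisher's test with exactly one positive and 3 responders. The plan's own Pearson test gives p = 0.025 on that table, and two positives can suffice under Fisher. Two or more positives has probability 64-84% under the assumed frequency.

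Patients below 10% at baseline have little room to fall on any scale, so part of the insensitivity to decreases is a floor rather than a coding loss. Hypothesis 2 puts its emphasis on ER beta, for which nothing can be quantified. Aim 2 is secondary, and the primary endpoint and the Simon decision are unaffected.

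**Conclusion.** The point holds as a mismatch between aim and scale. ER staining is categorised at 10% although Aims 2a and 2b and the planned correlation concern levels, and in the marker lesion this stain (ER alpha and ER beta-1) is the only pretreatment ER measure. Analysing it as yes/no discards much of the information on change and on the association with response.

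Two results need no distributional assumption: the reduction of both coefficients to phi in a 2x2 table of at most 17 patients, and the need for at least six crossings in one direction. The estimate of 2 to 3 ER alpha positives rests on the cited frequency applying at this cut, which the documents do not establish. The simulated powers rest on a normal scale, a Ki-67 effect size borrowed for ER, and assumed positivity and correlation. They show the direction and rough size of the loss, not a forecast. The documents do not support a claim that Aim 2 is unanswerable.

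**What to change.** Under Specific Aim 2a and 2b:

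- Record percent positive nuclei (0-100%) for each ER stained by immunohistochemistry, in every specimen.
- Use it as a continuous variable for the paired pre/post comparison in Aim 2a, with a paired t-test or its nonparametric counterpart, as for Ki-67 and TUNEL.
- Use it for the association with response in Aim 2b, for example Mann-Whitney between responders and non-responders, or Spearman.
- Keep the 10% category as a descriptive secondary summary.

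The cost is a few words of protocol text and one field on the reading form, since the percentage must be judged in any case to apply the cut. It should be settled before slides are read. A percentage not recorded then can be recovered only by re-reading, and the plan does not bank specimens and destroys them at the end of the trial (Collection of specimens; Samples Concerns).

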### **Risks:**

#### **Tamoxifen**

The manufacturer states that the adverse effect profile of tamoxifen in breast cancer patients generally appears to be similar for men and women. Adverse effects of tamoxifen citrate usually are relatively mild and rarely severe enough to necessitate discontinuance of the drug in patients with breast cancer. Tamoxifen usually is well tolerated in male patients with breast cancer.

1. **Cardiovascular Effects**  
Adverse cardiovascular effects of tamoxifen include thrombotic and venous thromboembolic events such as stroke, pulmonary embolism, and deep-vein thrombosis.
2. **Thromboembolic Events**  
In the BCPT (Breast Cancer Prevention Trial): women without a history of pulmonary emboli receiving tamoxifen had an approximately threefold increase in the risk of developing a pulmonary embolism (18 versus 6 cases; incidence rate of 0.75 versus 0.25 per 1000 women-years) compared with those receiving placebo. Although the difference was not significant, the risk of deep-vein thrombosis was increased (relative risk of 1.6) among women receiving tamoxifen versus placebo in the BCPT (35 versus 22 cases according to data available as of March 31,

1998). A similar increase in relative risk of deep-vein thrombosis was observed in women aged 49 years and younger as in women aged 50 years or older, although fewer events occurred in younger women. Although the difference was not significant, an increase in the incidence of stroke was observed in women receiving tamoxifen (38 events) versus placebo (24 events) in the BCPT (relative risk of 1.59 and 95% confidence interval of 0.93-2.77 according to data available as of March 31, 1998).

3. **Vasomotor Symptoms**  
In clinical studies, vasomotor symptoms (i.e., hot flushes [flashes]) occur more frequently in patients receiving tamoxifen than in those receiving placebo. In the BCPT, hot flushes occurred in 81% of women receiving tamoxifen compared with 69% of those receiving placebo.
4. **Effects on Lipoproteins**  
Hyperlipidemias have been reported in patients receiving tamoxifen. Hypertriglyceridemia has been reported in patients with breast cancer receiving tamoxifen and may be severe, particularly in patients with a known history of elevated triglyceride levels, such as those associated with familial hypertriglyceridemia.
5. **Other Cardiovascular Effects**  
Fluid retention has been reported in women receiving tamoxifen as adjuvant therapy for breast cancer. Edema has also been reported in women with metastatic breast cancer receiving tamoxifen.
6. **Genitourinary and Renal Effects**  
Vaginal discharge and menstrual irregularities occur more frequently in patients receiving tamoxifen than in those receiving placebo. Vaginal discharge, occurring in 55%, was one of the most common adverse effects reported among women receiving tamoxifen for the primary prevention of breast cancer in the BCPT. Loss of libido and impotence have been reported in some male patients and resulted in discontinuance of tamoxifen therapy. Increased serum BUN and/or creatinine have also been reported in patients receiving tamoxifen as adjuvant therapy for breast cancer.
7. **Musculoskeletal Effects**  
Musculoskeletal pain and bone pain have been reported in patients with breast cancer receiving tamoxifen. Increased bone and tumor pain or flare have occurred with tamoxifen therapy for metastatic breast cancer and are sometimes associated with a good tumor response. Patients with increased bone pain may require additional analgesics. Hypercalcemia, in some cases life-threatening, may occur during initial tamoxifen therapy in patients with metastatic breast cancer who have bone metastases. A potentially beneficial estrogenic effect of prolonged tamoxifen therapy is preservation of bone mineral density of the lumbar spine in postmenopausal women.

8. **Ocular Effects**  
Tamoxifen rarely has been associated with ocular toxicity. Retinopathy, corneal opacities, and decreased visual acuity have occurred in patients receiving extremely high dosages (e.g., 180-320 mg daily) of tamoxifen for longer than 1 year. Ocular effects such as visual disturbances, decrement in color vision perception, corneal changes, cataracts, need for cataract surgery, optic neuritis, retinal vein thrombosis, intra-retinal crystals, posterior subcapsular opacities, and/or retinopathy have also been reported in patients receiving recommended dosages of the drug.
9. **Hepatic Effects**  
Changes in hepatic enzyme concentrations (e.g., increased serum AST [SGOT] or ALT [SGPT] concentrations) and increased bilirubin and/or alkaline phosphatase concentrations have been reported in patients receiving tamoxifen therapy. Rarely, more severe hepatic abnormalities, including fatty changes in the liver, cholestasis, hepatitis, hepatic necrosis, and death, have occurred.
10. **Gastrointestinal Effects**  
Adverse GI effects of tamoxifen, including nausea, anorexia, distaste for food, and abdominal cramps, have been reported in patients with breast cancer.
11. **Nervous System Effects**  
Adverse nervous system effects reported in patients receiving tamoxifen for metastatic breast cancer include dizziness, lightheadedness, headache, fatigue, and mental depression.
12. **Hematologic Effects**  
Thrombocytopenia (platelet counts of 50,000-100,000/mm^3 and, infrequently, lower) occasionally has occurred in patients receiving tamoxifen for the treatment of breast cancer; however, platelet counts returned to normal even though tamoxifen therapy was continued. Hemorrhagic episodes have occurred rarely in patients with severe thrombocytopenia. Neutropenia, pancytopenia, and leukopenia (white blood cell count less than 3000/mm^3), sometimes associated with anemia and/or thrombocytopenia, also have been reported and may be severe.
13. **Dermatologic Effects**  
Thinning and/or partial loss of hair occurs infrequently in patients receiving tamoxifen for metastatic breast cancer. Erythema multiforme, Stevens-Johnson syndrome, and bullous pemphigoid have been reported rarely in patients receiving tamoxifen.
14. **Other Adverse Effects**  
Other adverse effects reported in patients receiving tamoxifen as adjuvant therapy for breast cancer or for metastatic breast cancer include weight loss, fatigue, and

cough.

15. Geriatric Precautions

In the BCPT, 16% of the study participants were 65 years of age or older and 6% were at least 70 years of age. Reductions in the incidence of breast cancer were observed in women receiving tamoxifen across all age groups. Across all other outcomes, the results in the subset of women 65 years of age or older reflect the results observed in the subset of women at least 50 years of age. In this trial, the risk of serious adverse effects (e.g., endometrial cancer, pulmonary embolism, deep-vein thrombosis, stroke) was greatest in women 50 years of age and older.

16. Carcinogenicity

- Uterine Cancer

An increased incidence of uterine cancer, sometimes fatal, has been reported in women receiving tamoxifen. Most uterine malignancies associated with tamoxifen therapy are classified as adenocarcinoma of the endometrium; however, rare uterine sarcomas, including malignant mixed mullerian tumors, also have been reported. Uterine sarcoma has been reported more frequently among women receiving long-term therapy (i.e., exceeding 2 years) with tamoxifen than among women not receiving the drug. Among women enrolled in the BCPT, uterine sarcomas were reported in 4 women receiving tamoxifen versus none of the women receiving placebo (an incidence of 0.17 and 0 per 1000 women-years, respectively). Uterine sarcoma generally is associated with more advanced disease at the time of diagnosis, poorer prognosis, and shorter survival. After approximately 6.8 years of follow-up in the National Surgical Adjuvant Breast and Bowel Project (NSABP B-14) study, 15 of 1419 women randomized to receive tamoxifen 20 mg daily for 5 years developed uterine cancer; 2 of 1424 women who were receiving placebo initially, but who subsequently received tamoxifen for recurrent breast carcinoma, also developed uterine cancer. The relative risk of endometrial cancer in the tamoxifen-treated women was 7.5; most of the uterine cancers in tamoxifen-treated patients with breast cancer were diagnosed at an early stage, but deaths resulting from uterine cancer associated with tamoxifen therapy for the treatment of breast cancer have been reported. Endometrial hyperplasia can be a premalignant change. In one study of postmenopausal women receiving tamoxifen for the prevention of breast cancer, 16% developed atypical hyperplasia while no cases occurred in those receiving placebo; 8% of women receiving tamoxifen had an endometrial polyp compared with 2% of those receiving placebo. Endometriosis also has been reported. The manufacturer states that patients receiving or having previously received tamoxifen should undergo routine gynecologic examinations, and they should be advised to report promptly any menstrual irregularities, abnormal vaginal bleeding, change in vaginal discharge, or pelvic pain/pressure to their clinician; the cause of

such effects should be evaluated promptly.

- Liver Cancer  
In a study of women with breast cancer receiving tamoxifen (40 mg daily) or no adjuvant endocrine therapy for 2-5 years, 3 cases of liver cancer were reported in women receiving tamoxifen versus 1 case in the control group. No cases of liver cancer currently have been reported (at a median follow-up of 4.6 years) among women receiving either tamoxifen or placebo in the BCPT.

17. Pregnancy, Fertility, and Lactation

- Pregnancy

Tamoxifen may cause fetal harm when administered to pregnant women. Effects on reproductive function are expected from the antiestrogenic properties of the drug. Although the clinical importance of these changes is unknown, some of these changes, especially vaginal adenosis, are similar to those observed in young women who were exposed to DES in utero; such women have a greater risk (1 in 1000) of developing clear-cell adenocarcinoma of the vagina or cervix. To date, in utero exposure to tamoxifen has not been shown to cause vaginal adenosis or clear-cell adenocarcinoma of the vagina or cervix in young women. There are no adequate and well-controlled studies using tamoxifen in pregnant women. There have been reports of spontaneous abortions, birth defects, fetal deaths, and vaginal bleeding. Women should not become pregnant while receiving the drug, and those of childbearing potential should use an effective barrier or other nonhormonal method of contraception during tamoxifen therapy. When tamoxifen is administered during pregnancy or if the patient becomes pregnant while receiving the drug or within approximately 2 months after discontinuance of therapy with tamoxifen, the patient should be informed of the potential hazard to the fetus, including the possible long-term risk of a DES-like syndrome. For sexually active women of childbearing potential who are receiving tamoxifen for reduction in the incidence of breast cancer, therapy with the drug should be initiated during menstruation. In women with menstrual irregularity, pregnancy testing with a negative a-HCG should be confirmed immediately prior to the initiation of tamoxifen therapy.

- Fertility

A decreased number of implantations, as well as death of all fetuses, was observed in reproduction studies in male and female rats receiving tamoxifen.

- Lactation

It is not known if tamoxifen is distributed into milk. Because of the potential for serious adverse reactions to tamoxifen in nursing infants, a

decision should be made whether to discontinue nursing or the drug, taking into account the importance of the drug to the woman.

